1 BACKGROUND

Migraine is common in children and adolescents. It affects 5% of children by age ten and prevalence increases further in adolescence. In addition to causing pain, migraine causes children and teens to miss school and can impact their school performance. While acute medications exist for treating migraine in children and adolescents, they do not work for all children and can cause significant side effects. In addition, some patients and parents prefer a natural supplement for acute migraine treatment rather than a prescription or over-the-counter pharmacologic agent (e.g. sumatriptan or ibuprofen). Additional safe, well- tolerated and effective acute migraine treatments are needed to help those who do not respond to existing therapies, experience significant side effects from existing therapies, or who prefer not to be taking prescription acute medications.

1.1 Overview of Non-Clinical Studies

Melatonin is a well-known and well-established substance, and there are no relevant non-clinical studies or safety concerns pertinent to using this drug for a migraine indication.

1.2 Overview of Clinical Studies

Melatonin is effective for migraine prevention in adults and data suggest it may also be effective for migraine prevention in children and adolescents. Our clinical experience suggests melatonin may also be helpful for treating *acute* migraine in children and adolescents, even among some who do not respond to other acute agents. There are several possible mechanisms by which melatonin might help migraine acutely. Melatonin may help children get to sleep, and sleep seems to be helpful in terminating migraine attacks. Melatonin may also have direct, acute analgesic effects. It has been used to treat acute procedural pain in children, without significant safety issues, even when administered at a high-dose of 10mg/kg IV to neonates who were undergoing endotracheal intubation (i.e. a dose of about 30 mg IV for a typical 3 kg neonate). There are melatonin receptors in both the thalamus (part of the ascending nociceptive pathway) and the periaqueductal grey (part of the descending anti-nociceptive pathway). There are also melatonin receptors in the hypothalamus, a part of the brain thought to be involved in generating migraine attacks. In animals, melatonin has been shown to decrease the amount of trigeminal nociceptive activation induced by cortical spreading depression, suggesting it could be effective acutely for migraine.

It is already established that certain agents that are traditionally thought of as useful for migraine prevention can also be useful for treating acute migraine—such as sodium valproate. The reverse also appears to be true, for example the NSAID naproxen is effective for acute migraine treatment but also can be effectively used as a migraine preventive. The question now arises whether melatonin—known to be effective for migraine prevention in adults and likely in children—can also be effective acutely for migraine.

This proposed pilot trial is a dose finding study to determine which dose of melatonin is most effective at treating acute migraine in children and adolescents who have episodic migraine. The

doses being studied here are well within the range of what has been safely studied in children before. We propose, depending on weight, to give between 1 mg and 8 mg of melatonin, once, at onset of headache. Each participant would treat two attacks. As noted above, neonates have safely been given 10mg/kg IV for peri-procedural pain management. Children undergoing auditory brainstem response tests were given 5-20 mg. Doses of 0.25-0.5 mg/kg have been given for MRI sedation—which would equate to about 15 mg for a 30 kg child. In another study, children were given 10 mg for MRI sedation. Our clinical experience suggests that for acute migraine treatment, 1-4 mg of melatonin would be adequate for children < 40 kg, and 2-8 mg for children and adolescents >40 kg. We propose to study a melatonin formulation that is an edible (i.e. chewable) milk-chocolate based formulation. We consider this formulation to have three potential advantages:

1. More rapid onset than a tablet/capsule formulation, potentially allowing for faster relief and in turn potentially a higher chance of relief, as treating when the pain is still mild has been shown to predict efficacy of other acute migraine treatments.
2. Young children who cannot yet swallow pills will be able to take this formulation.
3. Children who are nauseated during migraine attacks may still find a chocolate-based formulation palatable and be willing to take it during an attack.

2 STUDY RATIONALE

This pilot study is a dose finding study to determine what dose of melatonin seems effective for treating acute migraine in children and adolescents with episodic migraine. We will identify the most effective dose to pull forward into a future fully-powered placebo-controlled efficacy study. If doses are equally effective, we will bring forward the best tolerated dose. If equally well tolerated, we will bring forward the lowest effective dose, as this will minimize cost to families should this treatment become widely adopted.

2.1 Risk / Benefit Assessment

2.2 Very low risks to participating in this study, and inconvenience to the participant/family is minimized as most/all study activities can be completed from the participant's home.

3 STUDY OBJECTIVES

3.1 Primary Objective

To determine a change in mean VAS score between baseline and 2-hr time point in low-dose vs. high-dose group.

3.2 Secondary Objectives

- To determine a change in mean VAS score between baseline and 2-hr time point in low-dose vs. high-dose group in the < 40 kg and the ≥ 40 kg subgroups. (We will also do sensitivity analyses of completers who were awake for the 2-hr time point).

- To determine the tolerability/side effects of high-dose vs. low-dose in the group over all, and in weight-based strata.
- To determine the proportion of participants who get to mild/no pain by 2 hrs (overall and by weight group), and who remain at mild/no pain from 2-24hours
- To determine the proportion of participants who get to mild/no of each of: pain, photophobia, phonophobia, nausea, vomiting at 30, 60, 90, and 120 minutes and 24 hours; both overall and in weight based strata.
- To determine the proportion of parents/participants who found the treatment useful, and who preferred it over other treatments they'd tried.
- Using logistic regression, we will examine for possible predictors of treatment efficacy (sex, age, nap, nap duration, etc).
- To determine the proportion of participants who needed rescue medication between 2-24 hrs, both overall and by weight- based strata.

4 STUDY DESIGN

4.1 Study Overview

This randomized pilot trial is a dose finding study to determine which dose of melatonin is most effective for treating acute migraine in children and adolescents who have episodic migraine. Participants will be randomized to a higher-dose or a lower-dose, stratified by weight (< 40 kg and \geq 40 kg). They will treat 2 acute headache attacks and will complete a symptom diary for those 2 attacks and then return the diary to the study center. Randomization will be done in blocks of 4 to ensure equal group size and will be stratified by weight (< 40 kg or \geq 40 kg).

5 CRITERIA FOR EVALUATION

5.1 Primary Efficacy Endpoint

To determine in a randomized trial which dose of melatonin, “high dose” vs. “low dose”, is more effective at two-hours for acute migraine head pain in children and adolescents who have episodic migraine.

5.2 Secondary Efficacy Endpoints

- To determine a change in mean VAS score between baseline and 2-hr time point in low-dose vs. high-dose group in the < 40 kg and the \geq 40 kg subgroups. (We will also do sensitivity analyses of completers who were awake for the 2-hr time point).
- To determine the tolerability/side effects of high-dose vs. low-dose in the group over all, and in weight-based strata.
- To determine the proportion of participants who get to mild/no pain by 2 hrs (overall and by weight group), and who remain at mild/no pain from 2-24hours
- To determine the proportion of participants who get to mild/no of each of: pain, photophobia, phonophobia, nausea, vomiting at 30, 60, 90, and 120 minutes and 24 hours; both overall and in weight based strata.
- To determine the proportion of parents/participants who found the treatment

useful, and who preferred it over other treatments they'd tried.

- Using logistic regression, we will examine for possible predictors of treatment efficacy (sex, age, nap, nap duration, etc).
- To determine the proportion of participants who needed rescue medication between 2-24 hrs, both overall and by weight- based strata.

5.3 Safety Evaluations

Although there is substantial safety data for the use of melatonin in children and adolescents (as cited above), safety will be carefully monitored throughout this study by review of the headache diary forms by the investigator team.

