Chocolate melatonin supplies will be given to the parents for all young children who, in the opinion of the investigator, may need additional supervision. If a child were to eat all of the chocolate melatonin pieces at once, this would still be considered a safe amount, as neonates have been safely given 10mg/kg IV melatonin³.

They will also be given a paper headache diary (either in person or shipped). They will be instructed to treat as early as possible in an attack, i.e. ideally while the pain is still mild, however they will still be permitted to treat even if the pain has reached the moderate or severe levels. Participants will be asked to treat attacks that occur at home (or attacks that are not yet treated when they reach home), or that occur at another location where they can stay for at least 8 hours if needed, so as to ensure driving after dosing will not be necessary (for older teens), and that headache diaries will be available, and participants can sleep after dosing if desired.

Participants will record baseline pain intensity (and other migraine symptom intensity) at time zero, i.e. right before they dose the melatonin. They will be asked not to take other acute medications for two hours, and to record pain intensity (and other symptom intensity) at 30, 60, 90 min and the two-hour time marks. If they fall asleep, parents/caretakers will be instructed **not** to wake them for data collection, as sleep may be a mechanism by which melatonin helps acute

migraine. They will resume data collection as soon as they first awaken. They will be asked to collect data also at 4 hours and 24 hrs, and to record any acute medication used between 2-24 hours. They will also be asked to record their impressions about the treatment's efficacy, side effects, and whether or not they slept after dosing and if so for how long.

Study staff will contact participants until they complete the study to remind them about when to treat an acute attack and to answer any questions. Participants may be sent 'retention' packages (small office supplies, pens, or other small items) to remind them about the study. At the completion of the study, participants will be asked to mail back the headache diary in a pre-paid FedEx envelope. A \$5 gift card will be given to participants once they mail back the diary.

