11 ADVERSE EXPERIENCE REPORTING AND DOCUMENTATION

11.1 Adverse Events

An adverse event (AE) is any untoward medical occurrence in a clinical investigation of a patient administered a pharmaceutical product and that does not necessarily have a causal relationship with the treatment. An AE is therefore any unfavorable and unintended sign (including an abnormal laboratory finding), symptom or disease temporally associated with the administration of an investigational product, whether or not related to that investigational product. An unexpected AE is one of a type not identified in nature, severity, or frequency in the current protocol or of greater severity or frequency than expected based on the information in the protocol.

The study team will collect AE information in the headache diary data. Adverse events will be recorded in the patient CRF. Adverse events will be described by severity, outcome, treatment and relation to study drug, or if unrelated, the cause.

AE Severity

The National Cancer Institute's Common Terminology Criteria for Adverse Events (CTCAE) Version 3.0 should be used to assess and grade AE severity, including laboratory abnormalities judged to be clinically significant. The modified criteria can be found in the study manual. If the experience is not covered in the modified criteria, the guidelines shown in

Table 1 below should be used to grade severity. It should be pointed out that the term "severe" is a measure of intensity and that a severe AE is not necessarily serious.

Table 1. AE Severity Grading

Severity (Toxicity Grade)	Description
Mild (1)	Transient or mild discomfort; no limitation in activity; no medical intervention or therapy required. The subject may be aware of the sign or symptom but tolerates it reasonably well.
Moderate (2)	Mild to moderate limitation in activity, no or minimal medical intervention/therapy required.
Severe (3)	Marked limitation in activity, medical intervention/therapy required, hospitalizations possible.
Life-threatening (4)	The subject is at risk of death due to the adverse experience as it occurred. This does not refer to an experience that hypothetically might have caused death if it were more severe.

AE Relationship to Study Drug

The relationship of an AE to the study drug should be assessed using the following the guidelines in Table 2.

Table 2. AE Relationship to Study Drug

Relationship to Drug	Comment

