12 DISCONTINUATION AND REPLACEMENT OF SUBJECTS

12.1 Early Discontinuation of Study Drug

A subject may be discontinued from study treatment at any time if the subject, the subject's parent/guardian, or the investigator think that it is not in the subject's best interest to continue.

If a subject is withdrawn from treatment due to an adverse event, the subject will be followed and treated by the Investigator team until the abnormal parameter or symptom has resolved or stabilized.

All subjects who discontinue study treatment should tell the study site.

All subjects are free to withdraw from participation at any time, for any reason, specified or unspecified, and without prejudice.

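### Diary review cannot monitor safety between a participant's two attacks, because the single paper diary comes back only after both; the planned staff contacts could cover the gap

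*Combined protocol and SAP*

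**What the plan says.** Section 5.3 names one tool and one time frame for safety: "safety will be carefully monitored throughout this study by review of the headache diary forms by the investigator team". Section 11.1 gives the diary the same role: "The study team will collect AE information in the headache diary data".

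Section 10.1 describes the diary: "They will also be given a paper headache diary (either in person or shipped"). Section 4.1 says that participants "will complete a symptom diary for those 2 attacks and then return the diary to the study center". Section 10.1 gives the same timing: "At the completion of the study, participants will be asked to mail back the headache diary in a pre-paid FedEx envelope".

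Other routes are described as well:
- Section 9.1.6 lets participants and parents report adverse events at any time, with details recorded on the CRF.
- The synopsis, in the row on planned interim analyses, has serious adverse events monitored on an ongoing basis by the principal investigator and the IRB.
- Section 10.1 plans contact during participation: "Study staff will contact participants until they complete the study to remind them about when to treat an acute attack", and to answer questions.

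Section 12.1 allows treatment to be stopped if the participant, a parent or guardian, or "the investigator think that it is not in the subject's best interest to continue".

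**The concern.** A paper diary tells the site nothing until it is returned. If one diary holds both attacks and is returned after the second, its review cannot inform anything that happens between them.

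Three things depend on that information:
- **Discontinuation.** The investigator's option in section 12.1 has no routine source of attack 1 information behind it. It has only what families choose to report.
- **Quality of adverse event data.** Section 9.1.6 asks for start and stop times, severity, outcome, treatment and relation to study drug. If staff first see an attack 1 event after attack 2, they must clarify it late. Eligibility requires an average of at least one attack per month, so the delay could be weeks.
- **Completeness of the tolerability comparison.** Tolerability is a secondary objective, and under section 2 it decides which dose goes forward if the doses are equally effective. The safety population in section 14 includes anyone who took at least one dose. A participant who treats attack 1 and never returns the diary belongs to that population but contributes no diary data on side effects.

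**Working it through.** The main point is one of timing and needs no arithmetic. The sequence for one participant is:

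1. The bottles for attack 1, attack 2 and the extra pieces are all provided at the start (section 10.1). Supply for attack 2 does not depend on any review of attack 1.
2. Attack 1 is treated and entered in the paper diary.
3. At least 24 hours free of headache must pass (section 10.1). No safety review is described for this interval.
4. Attack 2 is treated and entered in the same diary.
5. The diary is mailed back (sections 4.1 and 10.1).
6. Diary review first becomes possible.

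Step 6 always follows step 4, so attack 1 diary entries cannot be reviewed before attack 2 dosing.

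The other routes compare with this sequence as follows:

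| Route | Can act before attack 2? | What it covers |
|---|---|---|
| Diary review (5.3, 11.1) | No | All diary-recorded events, after return |
| Spontaneous report (9.1.6) | Yes | Events the family volunteers |
| Ongoing SAE monitoring (synopsis) | Yes, once the team knows of the event | Serious events only |
| Staff contacts (10.1) | Possibly; timing not stated | Reminders and questions; asking about events is not described |

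What remains uncovered is a non-serious attack 1 event that is recorded in the diary and not volunteered.

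For diaries that never come back, the documents give only the planning drop-out of 15% (synopsis). Applied to the 76 participants of the sample size rationale, this is 0.15 × 76 = 11.4, or about 11. Applied to the 100 in the synopsis row on number of subjects, it is 0.15 × 100 = 15. The documents do not say how many drop-outs would already have taken a dose. If drop-out stands for non-return of the diary, which is an assumption, the number of dosed participants with no diary review lies between 0 and about 11 (or 15).

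**The case against.** The strongest reply is that section 5.3 speaks of the study, not of the interval between one child's attacks. Enrollment runs over 24 months. Completion most naturally means each participant's own completion, since the gift card follows return of that participant's diary. Diaries can then be reviewed as they arrive, and section 5.3 holds across the trial. This stands. A reader might infer a flat contradiction between sections 5.3 and 10.1, but the documents do not support that.

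Nor do they support the inference that attack 1 events in general go unseen before attack 2. Families can report at any time, serious events are monitored continuously, and staff are in touch with participants. The study is open label, so the family knows the dose, observes attack 1 directly and may stop treatment itself. The protocol also describes the risks as very low.

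Silence has limits as evidence too. Text following section 11.2.1 is not in the available copy, and neither are the diary or the study manual. One can say that asking about events at the contacts is not described, not that it would not happen.

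What survives is narrower: within a participant, the one systematic source of adverse event data is retrospective, and the earlier routes described rely on the family volunteering the event or on its being serious.

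**Conclusion.** The point holds within a participant. Attack 1 events that are recorded only in the diary and not volunteered under section 9.1.6 are not reviewed before attack 2, and are not reviewed at all if the diary is not returned. The timing applies to everyone who treats two attacks under the planned flow. The number of events involved cannot be estimated, because the documents give no event rate.

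The conclusion rests on two assumptions: that the diary is returned once, as sections 4.1 and 10.1 describe, and that no between-attack questioning is specified in material outside the available copy. It does not show that safety oversight is absent or that participants are exposed to a demonstrated hazard. It is best treated as a cheap improvement to data flow and wording.

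**What to change.** Reconcile sections 5.3, 9.1.6, 10.1 and 11.1:

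- In section 10.1, add to the staff contacts already planned that, once attack 1 has been treated, staff ask the diary's side-effect questions and record the answers on the CRF.
- In section 5.3, say that diary review is retrospective for each participant, and that these contacts and spontaneous reports are the earlier route.

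This also secures attack 1 side-effect data from participants who are reached but never return a diary. It will not always precede attack 2, because the two attacks may be little more than 24 hours apart; section 5.3 should not promise more than that. No dose, stopping rule or condition for treating attack 2 is proposed.

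The cost is a short set of questions, a wording change and a few minutes of staff time per participant.

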6 SUBJECT SELECTION

6.1 Study Population

Subjects ages 3-17 inclusive with a diagnosis of episodic migraine who meet the inclusion and exclusion criteria will be eligible for participation in this study.

6.2 Inclusion Criteria

1. Meet ICHD criteria for episodic migraine in children and adolescents, with at least 1 migraine attack per month on average.
2. Age 3-17 years
3. Dissatisfaction with previous acute treatments, for one or more of the following reasons: a) One or more previously tried acute medications have not been effective, or adequately effective, b) previously tried acute treatments have caused side effects, or C) patient/family would prefer a natural supplement for acute treatment over medication treatment.
4. If of driving age, teen participant agrees not to drive for at least 8 hours after treating with melatonin.

6.3 Exclusion Criteria

1. Allergy or intolerance to melatonin, or to chocolate.
2. Opioid or barbiturate overuse as defined in ICHD
3. Pregnant/lactating

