8.3 Formulation of Test and Control Products

8.3.1 Formulation of Test Product

Chocolate melatonin pieces, developed by Good Day Chocolate

Table 1: Formulation of melatonin

	Melatonin
Active Ingredient, mg/mL	Melatonin 1mg per piece
Other ingredient, mg/mL	Chamomile extract

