8.3.2 Formulation of Control Product

There is no control product, all participants will receive chocolate melatonin.

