9.1.3 Medical History

Relevant medical history will be recorded at Screening.

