10 EVALUATIONS BY VISIT

10.1 Visit 1

Baseline data will be collected by either an investigator and/or the study coordinator either in-person in the clinic, via a recommendation by their doctor or another member of the study team, or via phone for those enrolling remotely. All participants will have already been verified to meet ICHD criteria for episodic migraine. Headache duration, history, preventive medication use pattern, acute medication use pattern, aura status, family history, associated symptoms, comorbidities, pregnancy status and other variables will be assessed via questioning either in the clinic, chart review or via phone/text.

Participants will be instructed to treat two migraine attacks with their assigned melatonin dose. For those randomized to either 1mg or 2mg, they will receive 4 extra pieces in case they drop or lose any, or would like to use a different headache to track in the event that they take the melatonin and then something comes up where they are unable to track that headache for 24 hours.

For those randomized to 4mg or 8mg, they will receive 8 extra pieces. Participants are instructed that they are able to keep any unused pieces for a future attack but will be asked to return the empty bottles. Families will be asked to write down on the front cover of the headache diary how many of the extra pieces were either kept for later attacks, or were lost/dropped/thrown away. Alternatively, the study team will ask the families and record this for them. The diary asks how many chocolate pieces were taken for each attack.

Migraine attacks should be separated by at least 24 hours' headache freedom in between.

Participants will be provided with the Good Day sleep chocolate product and told their randomly assigned dose (either 1mg or 4mg for under 40kg, and either 2mg or 8mg for greater than or equal to 40kg). They will be given three bottles:

- Bottle 1 is labeled **Attack #1** and will have their exact dose (as described above)
- Bottle 2 is labeled **Attack #2** will have their exact dose (as described above)
- Bottle 3 is labeled **Extra** and will have either 4 or 8 pieces so they can have enough extra pieces if they drop or lose some of the pieces from bottle 1 or 2, as well as so they can use some if they want to treat another attack (they have been instructed to only use the dose they are assigned to)

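### The allergy exclusion names melatonin and chocolate but omits chamomile extract, a listed ingredient of the study product

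*Combined protocol and SAP*

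**What the plan says.** Section 6.3 has three exclusions. The first is "Allergy or intolerance to melatonin, or to chocolate"; the other two concern opioid or barbiturate overuse and pregnancy or lactation. The synopsis gives the same three.

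Section 6.1 says that patients aged 3 to 17 with episodic migraine "who meet the inclusion and exclusion criteria will be eligible for participation in this study".

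Table 1 in section 8.3.1 gives the active ingredient as "Melatonin 1mg per piece" and the other ingredient as "Chamomile extract", with no amount. Section 8.3.2 states: "There is no control product, all participants will receive chocolate melatonin".

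On screening, section 9.1.3 says "Relevant medical history will be recorded at Screening". Section 10.1 lists the Visit 1 topics, ending with "comorbidities, pregnancy status and other variables will be assessed via questioning" in the clinic, by chart review, or by phone or text. Allergy is not named in that list.

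**The concern.** The protocol accepts that allergy to what is in the product should keep a child out. It applies this to two ingredients and leaves out a third that it lists itself, without giving a reason.

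The stated safety rationale does not fill the gap, because it is about melatonin alone. Section 1.2 cites earlier paediatric melatonin doses. Section 10.1 argues that eating all the pieces at once would be safe by pointing to intravenous melatonin in neonates. Neither addresses chamomile.

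What is at stake is an avoidable exposure. The children may be as young as 3, and section 10.1 says "Participants will be asked to treat attacks that occur at home" or at another place where they can stay. A reaction would probably occur with no study staff present.

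**Working it through.** No figure in the plan bears on this point, so the check is a comparison of the text, followed by simple arithmetic on exposure.

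**Ingredients against exclusions**

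| Ingredient | Where named | Covered by an exclusion? |
|---|---|---|
| Melatonin | Table 1, section 8.3.1 | Yes, exclusion 1 |
| Chocolate | Section 8.3.1, product description | Yes, exclusion 1 |
| Chamomile extract | Table 1, section 8.3.1 | No |

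**Could another rule exclude the child?**

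1. The remaining exclusions (medication overuse; pregnancy or lactation) are unrelated to ingredients.
2. The four inclusion criteria in section 6.2 cover diagnosis and attack frequency, age, dissatisfaction with earlier treatment, and an undertaking not to drive. None concerns allergy.
3. No criterion refers to product components in general, and none allows exclusion at the investigator's discretion.
4. Sections 12.1 and 12.3 let the investigator, parent or child stop treatment. That is a discontinuation rule and does not decide who may enrol.
5. Chamomile is mentioned nowhere else in the text available.

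Under section 6.1, a child with known chamomile allergy who meets the other criteria is therefore eligible.

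**Who is exposed, and to how much**

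- Participants: sections 8.3.4 and 14.5 give four arms of 19, so 4 × 19 = 76. The synopsis gives 100 as the number of subjects.
- Pieces, at 1 mg each, with the extra pieces set in section 8.3.3 (4 for the 1 mg and 2 mg arms, 8 for the 4 mg and 8 mg arms):

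| Dose per attack | Pieces over two attacks | Pieces dispensed with the extra bottle |
|---|---|---|
| 1 mg | 2 × 1 = 2 | 2 + 4 = 6 |
| 2 mg | 2 × 2 = 4 | 4 + 4 = 8 |
| 4 mg | 2 × 4 = 8 | 8 + 8 = 16 |
| 8 mg | 2 × 8 = 16 | 16 + 8 = 24 |

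**How many children might be affected**

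The documents do not give the frequency of chamomile allergy. Purely for scale, assume 0.1% to 1% of enrolled children have it:

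- of 76: 76 × 0.001 = 0.08 to 76 × 0.01 = 0.76 children;
- of 100: 100 × 0.001 = 0.1 to 100 × 0.01 = 1.0 child.

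This range has no anchor in the documents, and the conclusion does not depend on it.

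**The case against.** The best case on the other side accepts the gap in the wording and disputes its weight.

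- **Consequence not shown.** The documents do not say how much chamomile is in a piece, how often children are allergic to it, or that it causes reactions. Only a child with a known allergy is affected. This stands, and it is why the point is minor.
- **Being eligible is not the same as being dosed.** Section 9.1.4 says participants have been examined in the headache programme's clinical care. Relevant history is recorded, the Visit 1 list is open-ended, and parents receive oral and written information before consenting. Treatment can also be stopped before a first dose at home. These steps lower the risk. However, section 10.1 lets a coordinator collect baseline data, and allows this by phone for remote enrolment. No criterion tells that person what to do if the allergy is mentioned. The steps reduce the consequence without changing the rule.
- **Consent pages.** They were removed from the text reviewed and may carry an ingredient warning. Such a warning would answer much of the safety concern, but it would not amend section 6.3.
- **Drafting slip.** Nothing suggests that chamomile was left out on purpose, so this is better read as an oversight than as a considered choice. That is fair, and it makes the correction easier.

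**Conclusion.** The concern holds. As written, the eligibility rule admits a child with known allergy to an ingredient that the protocol lists. This is certain on the text. How often it would matter is unknown and probably seldom: less than one child among 76, and at most about one among 100, under the assumed 0.1% to 1% range. Whether families are warned in the consent form cannot be judged from the text available.

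The issue is one of participant safety. It has no bearing on the primary comparison, the sample size or the choice of dose. Severity is minor, and correcting it is a cheap improvement.

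**What to change.** In section 6.3 and in the synopsis, extend exclusion 1 beyond melatonin and chocolate with the words *or to any other ingredient of the study product, including chamomile extract*. Add a matching question to the Visit 1 baseline questioning, so that it is asked whether enrolment is in person or remote.

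The general phrase is preferable to naming chamomile alone because it also covers components not listed in Table 1. Section 1.2, for instance, describes the product as based on milk chocolate, and milk is not named among the exclusions.

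The cost is a few words in two places, one screening question, and IRB approval of the amendment under section 16.1. At most a very few children would be excluded.
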